6.4. BLINDING

6.4.1. Verification of blinding

The trial design is considered as open label trial so blinding is not applicable for this trial.

6.4.2. Unblinding during the clinical trial

Not applicable for this open label trial.

7. SUBJECT REPORTED OUTCOME, EFFICACY AND SAFETY ASSESSMENT

7.1. SUBJECT REPORTED OUTCOMES

The following Subject Reported Outcome (PRO) questionnaires should be filled out by the subjects. The investigator or delegate should check all questions of the PRO questionnaires for completeness prior to the subject leaving the office.

7.1.1. Quality of Life Questionnaire

At baseline **before** application of the investigational product, at Week 12 and at Week 16/Early termination subjects will complete a Dermatology Life Quality Index questionnaire (DLQI) or Children Dermatology Life Quality Index questionnaire (cDLQI) (for children age of ≤ 16 years) (see [Attachment 1](#)).

DLQI and cDLQI questionnaires will be used in local language.

7.1.2. Subject Satisfaction Questionnaire

At Week 12 and Week 16/Early termination, subjects will complete a satisfaction questionnaire regarding use of investigational product they used in this trial (see [Attachment 2](#)).

Subject satisfaction questionnaire will be translated in local language.

7.2. EFFICACY ASSESSMENTS

Clinical evaluations should be performed by the same evaluator (investigator or designee) throughout the clinical trial. If it is not possible to use the same evaluator to follow a subject, then evaluations should overlap for at least one visit in order to examine the subject together and discuss findings and this should be documented in the source documents. At least for the baseline assessments and the final assessments (Week 16/Early termination), the evaluator should be the same person.

The evaluated areas must be examined under the same conditions of light exposure at each visit (same angle to avoid shadow and same light source, i.e. artificial or daylight).

7.2.1. Investigator's global assessment of acne severity (IGA)

The evaluator will assess the severity of acne for the whole face of the subject using the scale described below. The evaluator will assess subject's acne severity at each visit by performing a static ("snapshot") evaluation of acne. The evaluator should make no reference to baseline or other previous visit when evaluating the subject's acne.

Category	Score	Description
Clear	0	Clear skin with no inflammatory or non-inflammatory lesions
Almost Clear	1	A few scattered comedones and a few small papules
Mild	2	Easily recognizable; less than half of the face is involved. Some comedones and some papules and pustules.
Moderate	3	More than half of the face is involved. Many comedones, papules and pustules. One small nodule may be present.
Severe	4	Entire face is involved. Covered with comedones, numerous papules and pustules. Few nodules may or may not be present.

For the **inclusion criterion** (subjects should have an IGA of 3 or 4).

7.2.2. Global Assessment of Improvement (GAI)

At Week 12 and Week 16/Early termination, the evaluator will evaluate the degree of acne improvement **versus baseline** using the Global Assessment of Improvement score as follows:

Category	Score	Description
Excellent improvement	0	All or nearly all signs and symptoms cleared (around and more than 90% improvement from Baseline). Whether no, or only minimal residual signs and symptoms remain
Very good Improvement	1	Majority of the signs and symptoms have resolved (about 75% improvement from Baseline)
Good Improvement	2	Significant improvement, but many signs and symptoms remain (about 50% improvement from Baseline)
Minimal Improvement	3	Slight overall improvement, but not clinically significant (about 25% improvement from Baseline)
No Change	4	Overall severity similar to Baseline
Worse	5	Worse than Baseline

7.3. SAFETY ASSESSMENTS

Safety assessments will be conducted for all subjects at the baseline visit (after the ICF has been signed) and every subsequent visit. The safety parameters include adverse events (AEs) and increase in Post inflammatory hyperpigmentation (PIH) and local tolerance severity.

7.3.1. Post inflammatory hyperpigmentation (PIH)

Post inflammatory hyperpigmentation (PIH) is mostly seen in subjects with skin phototypes IV to VI (according to T.B. Fitzpatrick's definitions). PIH lesions may represent the sequel of various

cutaneous disorders as well as therapeutic interventions. The shapes of these lesions closely follow the contours of the original inflammatory dermatosis. Severity of PIH of the treated areas on the face will be evaluated by the evaluator at each visit as follows:

Category	Score	Description
None	0	No post inflammatory hyperpigmentation
Very mild	1	Few areas of post inflammatory hyperpigmentation, very small in size and only very slightly darker than the surrounding skin
Mild	2	Several areas of post inflammatory hyperpigmentation; small in size and slightly darker than the surrounding skin
Moderate	3	Many areas of post inflammatory hyperpigmentation; medium in size and much darker than the surrounding skin
Severe	4	Large number of areas of post inflammatory hyperpigmentation; large in size and markedly darker than the surrounding skin.

Any increase of PIH score during the trial is to be reported as an Adverse Event.

7.3.2. Local tolerance assessment

Local cutaneous signs and symptoms (erythema, scaling, dryness and/or stinging/ burning) are possible during treatment with Adapalene 0.3% - BPO 2.5%.

The investigator will evaluate erythema, scaling, dryness and/or stinging/burning at each visit. The investigator will record stinging/burning after discussion with the subject regarding the previous application days. The investigator will ask an open-ended question, taking care not to influence the subject's answer, such as: "Have you experienced any sensations immediately following product application (within 5 minutes)?"

Erythema, scaling, dryness will be evaluated by the investigator, and stinging/burning will be recorded by the investigator after discussion with the subject. The four signs and symptoms will be graded at each follow up visit as follows:

Erythema – abnormal redness of the skin		
None	0	No erythema
Mild	1	Slight pinkness present
Moderate	2	Definite redness, easily recognized
Severe	3	Intense redness
Scaling – abnormal shedding of the stratum corneum		
None	0	No scaling
Mild	1	Barely perceptible shedding, noticeable only on light scratching or rubbing
Moderate	2	Obvious but not profuse shedding
Severe	3	Heavy scale production
Dryness – brittle and/or tight sensation		
None	0	No dryness
Mild	1	Slight but definite roughness
Moderate	2	Moderate roughness
Severe	3	Marked roughness
Stinging/Burning – pricking pain sensation immediately after dosing (within 5 minutes)		
None	0	No stinging/burning
Mild	1	Slight warm, tingling/stinging sensation; not really bothersome
Moderate	2	Definite warm, tingling/stinging sensation that is somewhat bothersome
Severe	3	Hot, tingling/stinging sensation that has caused definite discomfort

Note: *Stinging/Burning should NOT be assessed at the baseline visit*

An Adverse Event will be recorded if the severity of the signs and symptoms is such that:

- The subject's participation in the trial is interrupted at his/her request or at the investigator's request **after the first four weeks** of treatment.
- The subject permanently discontinues the treatment at his/her request or at the investigator's request.
- The subject requires concomitant prescription or OTC therapy (other than moisturizers).

Note: *Need for increased moisturizer use does NOT constitute an AE.*

Any new sign or symptom, which is not included in the scheduled evaluation of tolerability, should be recorded as an Adverse Event, including those of mild intensity.

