8. ADVERSE EVENT

8.1. DEFINITIONS

8.1.1. Adverse Events (AE)

According to ICH E2A, an AE is any untoward medical occurrence in a subject or clinical investigation subject administered a pharmaceutical product and which does not necessarily have a causal relationship with this treatment. An AE can therefore be any unfavorable and unintended sign (including an abnormal laboratory value), symptom, or disease temporally associated with the use of a medicinal (investigational) product, whether or not related to the medicinal (investigational) product.

Thus any new sign, symptom or disease, or clinically significant increase in the intensity of an existing sign, symptom or disease since the first visit (including the disease being treated), should be considered as an adverse event. Lack of efficacy should not be considered as an AE.

Each new episode of a chronic disease (e.g., hay fever, allergy, etc.) from the screening visit should be reported as a new AE.

Notes:

- Any new sign or symptom reported by the subject that appears after accidental or intentional overdose or misuse should also be reported as an AE.
- There should be an attempt to report a diagnosis rather than the signs, symptoms or abnormal laboratory values associated with the report of an AE. However, a diagnosis should be reported only if, in the Investigator's judgment, it is relatively certain. Otherwise, symptoms, signs, or laboratory values should be used to describe the AE.
- Pregnancy should not be considered as an adverse event but must be followed up as described in section 8.2.3.1.
- For an AE of irritation, the "date of onset" should be the date that the first symptom occurred.

There may be side effects during treatment with the investigational product, as described in the product monograph for Epiduo[®] Forte / TactuPump[™] Forte gel and in this protocol (mild to moderate application site reactions, such as skin irritation characterized by scaling, dryness, erythema, and burning/stinging).

The course of these expected events will be assessed and reported on the Local Tolerability Assessment Forms. An Adverse Event Form will be completed only if the severity of the expected signs and symptoms is such that an interruption (after the first 4 weeks of treatment)/discontinuation of the subject's participation in the clinical trial, at his/her request or at the investigator's, occurred and/or if a concomitant medication is prescribed to treat the sign/symptom(s).

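### Stinging/burning that starts more than 5 minutes after application falls under two conflicting recording rules, so it may be an adverse event at one site and in neither safety table at another

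*Combined protocol and SAP*

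**What the plan says.** Section 7.3.2 defines the graded item as "Stinging/Burning – pricking pain sensation immediately after dosing (within 5 minutes". The suggested question to the subject is "Have you experienced any sensations immediately following product application (within 5 minutes". The question is offered as an example, but the definition at the head of the scale is fixed.

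Section 8.1.1 names the expected effects as "mild to moderate application site reactions, such as skin irritation characterized by scaling, dryness, erythema, and burning/stinging", with no time limit on the burning. It continues: "The course of these expected events will be assessed and reported on the Local Tolerability Assessment Forms". It then restricts the AE form: "An Adverse Event Form will be completed only if the severity of the expected signs and symptoms is such that an interruption". The triggers that it allows are an interruption once week 4 has passed, a discontinuation, or medication, the last worded as "and/or if a concomitant medication is prescribed to treat the sign/symptom(s". Section 7.3.2 has a similar list of triggers, but also counts over-the-counter therapy other than moisturizers.

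The last paragraph of 7.3.2 gives a catch-all: "Any new sign or symptom, which is not included in the scheduled evaluation of tolerability, should be recorded as an Adverse Event". It applies to mild symptoms as well.

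Section 9.1.1 plans a local tolerance summary by visit with the worst score, and the incidence of AEs.

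**The concern.** The tolerability form grades burning over a shorter period than the one for which 8.1.1 relies on it. Section 8.1.1 can keep expected burning off the AE form because the tolerability form is meant to hold it. That form, by its own definition, takes only the first 5 minutes. The instructions for use in Section 6.1.5 list no rinse-off step after the evening application, so later sensations are possible, and the plan should say where they go.

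Three features make this matter here:

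- Good tolerability is part of the hypothesis in Section 3.2, and Section 2.1 describes these subjects as sensitive to topical retinoids.
- Stinging/burning is the only one of the four tolerance items recorded from discussion with the subject. The investigator evaluates the other three.
- Section 6.3.6 says local reactions are most likely in the first four weeks. In that period a temporary interruption does not trigger an AE form, so late burning has the fewest routes into a safety table.

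At stake are possible under-counting of local irritation and an AE incidence that depends partly on how each of the 4 sites reads the rules.

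**Working it through.** The plan states no figure on this point, so there is none to reproduce. The check follows a burning event through each recording rule to the two planned safety tables.

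| Case | Local tolerance table | AE table |
|---|---|---|
| (a) Starts and ends within 5 minutes | Yes, graded | Only with a listed consequence |
| (b) Starts within 5 minutes and persists | Presence and initial intensity graded; duration and later intensity not | Only with a listed consequence |
| (c) Starts after 5 minutes, with interruption after week 4, discontinuation or prescribed medication | No, outside the definition | Yes, under both 7.3.2 and 8.1.1 |
| (d) Starts after 5 minutes, with no listed consequence | No, outside the definition | Yes under the close of 7.3.2; no under 8.1.1 |

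Step by step for case (d):

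1. The scale definition in 7.3.2 excludes the event, so it has no grade on the tolerability form.
2. Under the catch-all in 7.3.2, the event is outside the scheduled assessment and is therefore an AE even if mild.
3. Under 8.1.1, burning is an expected event whatever its timing. Without a listed consequence, no AE form is completed.
4. Nothing in 7.3.2 or 8.1.1 says which of steps 2 and 3 prevails.
5. Section 7.3.3 makes all clinical medical events AEs, and Section 8.2.1 requires an open AE question at each post-baseline visit. These may bring the symptom to light, but 8.1.1 then directs expected burning to a form whose definition excludes it.

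Case (d) includes burning that leads only to an interruption in the first four weeks, or only to more moisturizer. Late burning treated only with an over-the-counter product is a border case: 7.3.2 lists it as a trigger, while 8.1.1 speaks of prescribed medication.

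Only case (d) can be missing from both tables, and only on the 8.1.1 reading.

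On size, the documents give no rate of burning and no share with onset after 5 minutes, so no count follows from them. For scale only, with about 60 subjects each one who moves into or out of a table changes a percentage by 1/60 = 1.7 points.

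**The case against.** The strongest reply is that the protocol, read as a whole, does capture late burning. The restriction in 8.1.1 follows directly on the sentence sending expected events to the tolerability form, so it can be read as covering only what that form assesses. The catch-all in 7.3.2 then takes the rest, supported by 7.3.3 and the open question in 8.2.1. That reading is reasonable, and the first remedy below makes it explicit. But 8.1.1 does not say so: it names burning/stinging without a time limit and uses restrictive wording. A site that follows it literally is not in error.

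It can also be said that other instruments have no 5-minute limit. DLQI item 1 asks about stinging over the last week, and satisfaction item 1 asks how bothersome side effects were. Dose modifications for local reactions go on the treatment compliance page (6.3.6). This is true, but none of these is a safety variable in 9.1.1 and none isolates late burning. After baseline, the questionnaires are collected only at Week 12 and Week 16 or early termination.

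Finally, grading immediate application stinging is a legitimate design choice, and in a single-arm descriptive trial no comparison or test is affected. Both points stand. They argue against dropping the 5-minute definition, not against saying where later burning is recorded.

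**Conclusion.** The concern holds as a conflict between recording rules. Burning that begins after 5 minutes and has no listed consequence may be recorded as an AE or in neither safety table, depending on which paragraph the site follows. For burning that begins within 5 minutes, only the later course is lost.

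A reader might go further in two ways that the documents do not support:

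- **That all burning after 5 minutes is missing from both tables.** Burning with a listed consequence reaches the AE table, burning with early onset is graded, and the catch-all in 7.3.2 can be read to take the remainder.
- **That the loss can be sized from the length of the window.** Five minutes out of 1,440 is 0.35% of the day, but that is a share of clock time, not of burning events. Any count of missed subjects would rest on rates that the documents do not contain.

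The direction is clear for a site that follows 8.1.1 literally: if late burning occurs there, local irritation is under-counted. The conclusion assumes only that some subjects have burning with onset after 5 minutes and that sites may read the two paragraphs differently.

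**What to change.** Reconcile 7.3.2 and 8.1.1 in one of two ways:

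1. In 8.1.1, limit the restriction on the AE form to signs and symptoms actually graded on the tolerability form. State in 7.3.2 that burning with onset after 5 minutes is outside the graded item and is recorded as an AE under the closing paragraph.
2. Keep the 5-minute grade and add an onset field (within or after 5 minutes) to the tolerability form. Extend the suggested question to match, tabulate late burning separately, and state that it then counts as part of the scheduled assessment so that it is not also reported by default as an AE.

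Whichever is chosen, align the medication trigger in the two sections (prescribed only, or over-the-counter as well).

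The cost is a sentence in each section and at most one extra field. Reported irritation or AE rates may be slightly less favourable. The 5-minute figure remains available under either option for comparison with trials that used that definition. No change to dosing or clinical management is involved.

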7.3.3. Adverse Events

Adverse Events will be recorded monitored throughout the course of the clinical trial. All clinical medical events, whether observed by the investigator or reported by the subject and whether or not thought to be product or trial procedure-related will be considered adverse events and

recorded on the appropriate adverse event form of the eCRF with complete information as required. If AEs occur, the main concern will be the safety of the subjects. At the time of the ICF signature, each subject must be provided with the name and phone number of clinical trial site personnel for reporting AEs and medical emergencies.

7.4. OTHERS

7.4.1. Cosmetic acceptability Questionnaire

At Week 16/Early termination, subjects will complete an acceptability questionnaire regarding the non-investigational product they have been using in this trial (see [Attachment 3](#)).

Subject cosmetic acceptability questionnaire will be translated in local language.

7.4.2. Photographs

Standardized digital photographs of the whole face (front, right and left) will be taken using a Canfield Scientific stereostatic device (Visia CR[®]) or equivalent. Detailed procedures will be provided. Subjects will be photographed at baseline and at each post-baseline visit.

At Baseline visit subjects' photograph will be used to confirm the severity of acne (moderate or severe) for inclusion of subjects into the trial. Sponsor Medical Expert will review the clinical evaluation of acne and give his confirmation for inclusion of subjects into the trial.

7.5. APPROPRIATENESS OF MEASUREMENTS

Efficacy is evaluated by assessing severity of acne by the investigator (IGA) and the degree of acne improvement versus baseline using the Global Assessment of Improvement (GAI) scores which are current and non-invasive techniques for assessing efficacy of acne treatment.

Post inflammatory hyperpigmentation (PIH) is mostly seen in subjects with skin phototypes IV to VI (according to T.B. Fitzpatrick's definitions). PIH lesions may represent the sequel of various cutaneous disorders as well as therapeutic interventions. Severity of PIH of the treated areas on the face will be evaluated by the the evaluator at each visit.

Acne can persist for years and may affect seriously the psychosocial development, resulting in emotional problems, withdrawal from society, and depression (Koo, J Y., et Smith, L L. 1991). If not treated, acne may cause serious physical and emotional scarring and can significantly impact the quality of life of those affected by the disease (Brown J.M., Poston S.M. 1983) (Usatine, RP., Quan, MA et Strick, R. 1998).

Therefore impact of trial treatments on subjects' quality of life will be assessed using quality of life and satisfaction questionnaires in dark skin subjects known to be sensitive with topical retinoids. For this, subjects will complete the DLQI / cDLQI at baseline, Week 12 and at the end of the trial. A satisfaction questionnaire will also be completed by all subjects at Week 12 and at the end of the trial Week 16/Early termination.

To collect specifically subject's feed-back on the associated non-investigational products used in the trial, a subject cosmetic acceptability questionnaire will be completed at the end of the trial Week 16/Early termination.

Safety will be assessed through the reporting of adverse events and local tolerability assessment on an ongoing basis as a well-established process in clinical trials.

8. ADVERSE EVENT

8.1. DEFINITIONS

8.1.1. Adverse Events (AE)

According to ICH E2A, an AE is any untoward medical occurrence in a subject or clinical investigation subject administered a pharmaceutical product and which does not necessarily have a causal relationship with this treatment. An AE can therefore be any unfavorable and unintended sign (including an abnormal laboratory value), symptom, or disease temporally associated with the use of a medicinal (investigational) product, whether or not related to the medicinal (investigational) product.

Thus any new sign, symptom or disease, or clinically significant increase in the intensity of an existing sign, symptom or disease since the first visit (including the disease being treated), should be considered as an adverse event. Lack of efficacy should not be considered as an AE.

Each new episode of a chronic disease (e.g., hay fever, allergy, etc.) from the screening visit should be reported as a new AE.

Notes:

- Any new sign or symptom reported by the subject that appears after accidental or intentional overdose or misuse should also be reported as an AE.
- There should be an attempt to report a diagnosis rather than the signs, symptoms or abnormal laboratory values associated with the report of an AE. However, a diagnosis should be reported only if, in the Investigator's judgment, it is relatively certain. Otherwise, symptoms, signs, or laboratory values should be used to describe the AE.
- Pregnancy should not be considered as an adverse event but must be followed up as described in section 8.2.3.1.
- For an AE of irritation, the "date of onset" should be the date that the first symptom occurred.

There may be side effects during treatment with the investigational product, as described in the product monograph for Epiduo[®] Forte / TactuPump[™] Forte gel and in this protocol (mild to moderate application site reactions, such as skin irritation characterized by scaling, dryness, erythema, and burning/stinging).

The course of these expected events will be assessed and reported on the Local Tolerability Assessment Forms. An Adverse Event Form will be completed only if the severity of the expected signs and symptoms is such that an interruption (after the first 4 weeks of treatment)/discontinuation of the subject's participation in the clinical trial, at his/her request or at the investigator's, occurred and/or if a concomitant medication is prescribed to treat the sign/symptom(s).

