6.3.6. Dose modification

Local cutaneous reactions including erythema, scaling, dryness, and stinging/burning may be experienced with use of Adapalene 0.3% - BPO 2.5%. All these adverse reactions are easily managed depending upon the severity of these adverse reactions.

Subjects should be instructed to use a moisturizer (the provided one for this trial) and if needed, investigators may reduce temporarily the frequency of the application of Adapalene 0.3% - BPO 2.5% (eg. every other day), or temporarily discontinue use.

These are most likely to occur during the first four weeks of treatment but are mostly mild to moderate in intensity, and usually improve with continued use of the medication. All dose modifications should be documented in the subject's source data and reported in the eCRF (treatment compliance page).

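### Sections 7.3.2 and 8.1.1 give different AE triggers for expected irritation, and section 9 plans no summary of worsening tolerance scores or of treatment reductions and pauses

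*Combined protocol and SAP*

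**What the plan says.** Section 6.3.6 lets investigators respond to local reactions by lowering the application frequency for a time, "eg. every other day), or temporarily discontinue use". It places most of these reactions in the first four weeks and requires each modification to be entered on the compliance page of the eCRF.

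Two sections then state when an expected reaction becomes an AE.

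- Section 7.3.2 has three triggers. The first is that the subject's "participation in the trial is interrupted at his/her request or at the" investigator's, and it applies only after the first four weeks. The second is "The subject permanently discontinues the treatment at his/her request" or the investigator's. The third is "The subject requires concomitant prescription or OTC therapy (other than moisturizers".
- Section 8.1.1 sends expected reactions to the tolerability forms. It adds an AE form "only if the severity of the expected signs and symptoms is such that an interruption (after the first 4 weeks of treatment)/discontinuation", which there relates to taking part in the trial. Its other trigger is "if a concomitant medication is prescribed to treat the sign/symptom(s".

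Section 7.3 names as safety parameters AEs and an increase in both post-inflammatory hyperpigmentation (PIH) and local tolerance severity. Section 9.1.1 plans a change from baseline for PIH. For local tolerance it plans raw scores, the worst score and the distribution of scores by visit. Section 9.1.3 adds AE tables and AE-related withdrawals. Neither lists a variable or table for frequency reductions, temporary interruptions or compliance. Section 9.1 defers detail to a separate SAP, which was not available for this review.

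**The concern.** The hypothesis in section 3.2 includes good tolerability. Three features of the plan weaken the evidence for it.

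- If two sections define the same AE differently, the incidence table depends partly on which one a site applied. With four sites in three countries, that cannot be told apart from a real difference.
- A worst score taken without reference to baseline counts erythema, scaling or dryness that was already there together with what arose on treatment.
- How many subjects had to reduce or pause the product is a direct descriptive measure of tolerability. It is collected, but the protocol plans no output for it, and a reader may take the AE table as a substitute.

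**Working it through.** **1. The AE rules side by side.** Each row is an event caused by an expected sign or symptom, with no other trigger present.

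| Event | 7.3.2 | 8.1.1 |
|---|---|---|
| Frequency reduction, any week | not listed | not listed |
| Temporary pause, weeks 0-4 | not a trigger | not a trigger |
| Temporary pause in use after week 4, subject still attending | trigger only if a pause in use counts as interrupted participation | same ambiguity |
| Permanent stop of product, if this does not also end participation | trigger | not a trigger as worded |
| Prescribed medication other than a moisturizer | trigger | trigger |
| OTC therapy other than a moisturizer | trigger | not a trigger as worded |

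The sections disagree in two rows (permanent stop, OTC therapy), and in one row both are unclear. In the first two rows they agree that the event by itself is not an AE.

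**2. Baseline comparison.** Erythema, scaling and dryness are scored at baseline. For the fourth sign, "Stinging/Burning should NOT be assessed at the baseline visit". A subject who goes from 1 at baseline to a worst score of 1 and a subject who goes from 0 to 1 are tabulated alike. The planned baseline distribution does not resolve this. Suppose, purely as an assumption, that 12 of 60 subjects score 1 at baseline, 12 of 60 score 1 at Week 2, and all others score 0. The number who worsened is 0 if they are the same 12 subjects and 12 if they are different ones (possible because 12 + 12 = 24, which is below 60). The planned tables look the same at those two visits in both cases.

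**3. What scheduled scoring sees early.** Inputs are the visit days and windows in section 5.4. Four weeks is day 28, Week 2 is day 14 (13 to 15) and Week 8 is day 56 (53 to 59).

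- Week 2 is the only scored post-baseline visit in the first 28 days. Days left after it: 28 - 14 = 14 (28 - 15 = 13 to 28 - 13 = 15).
- Gap to the next scored visit: 56 - 14 = 42 days (53 - 15 = 38 to 59 - 13 = 46).
- Part of the gap is covered for one symptom: "The investigator will record stinging/burning after discussion with the subject regarding the previous application days". A score, however, does not show that treatment was changed.

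**4. How far the AE table and the number of modifiers could part.** The documents give no rate, so the inputs are assumptions. Let M be the subjects who modify treatment for intolerance and f the share whose only consequence is a pause in weeks 0-4. Assume that all the others meet some AE trigger. Then the number in the AE table is M x (1 - f), an average where not whole, with N = 60.

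| M | f = 0.25 | f = 0.50 | f = 0.75 |
|---|---|---|---|
| 6 (10%) | 4.5 (7.5%) | 3 (5%) | 1.5 (2.5%) |
| 12 (20%) | 9 (15%) | 6 (10%) | 3 (5%) |
| 18 (30%) | 13.5 (22.5%) | 9 (15%) | 4.5 (7.5%) |

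The difference, M x f, runs from 6 x 0.25 = 1.5 to 18 x 0.75 = 13.5 subjects. Subjects who only reduced frequency would widen it. Each subject is 1/60 = 1.7 percentage points.

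**The case against.** A reader might infer that AE incidence is biased downward. The documents do not support that. The four-week exemption stands in both sections and looks deliberate, because expected reactions are sent to the tolerability forms and those scores are tabulated. An AE table that follows its own definition is not biased; it simply measures something else.

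A reader might also infer that early pauses can never be AEs. They can, if the stop becomes permanent or therapy is needed. A suspected allergic contact reaction is reportable under 8.2.3 with no week limit. Section 8.1.1 also describes the expected reactions as mild to moderate and does not say whether the exemption reaches severe ones.

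Nor is early irritation lost. The Week 2 scores and worst scores capture part of it. The compliance review in 6.3.3 and item 1 of the satisfaction questionnaire, on being bothered by side effects, also bear on tolerability. None of these tabulates treatment modifications, and the questionnaire comes at Week 12 and Week 16 or early termination.

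On OTC therapy, 4.5.2 includes OTC products among therapies, and 4.5.3 generally asks for an AE form when a new therapy is linked to an AE. That leans towards including OTC therapy, but the restrictive wording of 8.1.1 remains, so the conflict is reduced and not removed.

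Finally, the SAP may add what section 9 lacks. That stands: the claim is only that the protocol does not pre-specify it.

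**Conclusion.** The point holds in three limited parts. The AE triggers in 7.3.2 and 8.1.1 conflict on OTC therapy and on stopping treatment as against participation, and together with 6.3.6 they leave pauses after week 4 unclear. The increase in local tolerance severity named in 7.3 has no matching variable in 9.1.1. Recorded reductions and interruptions have no planned summary, and the AE table cannot stand in for one.

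The size cannot be determined from the documents; the table of assumed rates shows a possible range and is not an estimate. The conclusion rests on the protocol text alone. Safety is a secondary aim of a descriptive, open-label, single-treatment trial, and the quality-of-life and satisfaction results are not affected. The changes are worth making before the SAP is finalized, but nothing here undermines the trial's main purpose.

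**What to change.** 1. Reconcile 7.3.2 and 8.1.1 on the medication and discontinuation triggers, and both with 6.3.6 on participation, treatment and use. This review takes no position on which rule is right. Footnote the AE table with the reconciled rule.
2. Add to 9.1.1, on the safety population (APT), n (%) of subjects whose worst post-baseline erythema, scaling or dryness score exceeds baseline, by sign, and n (%) with any stinging/burning score above 0, since that symptom has no baseline.
3. Add, on the same population, n (%) with at least one recorded frequency reduction and n (%) with at least one temporary interruption, overall and for weeks 0-4 where recorded dates allow.

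The cost is one or two descriptive tables from data mostly collected already, and a notice to sites on the reconciled wording. The tolerability picture may look less favourable. The weeks 0-4 split may be incomplete, because the protocol does not say that dates of modifications are captured, and the diary may not separate a missed dose from a directed reduction.
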